Pregabalin vs. Gabapentin on Reducing Opioid Usage in Trauma Patients

NCT# 04705480

Protocol

IRB Approval Date: 07/22/2024

Title: Pregabalin vs. Gabapentin on Reducing Opioid Usage in Trauma Patients

Abstract

The pain following trauma can be difficult to manage because it can have more than one cause and differ from patient to patient. It is not uncommon for trauma patients to have localized pain related to their injuries coupled with a component of nerve pain. Pregabalin and gabapentin have both been effectively used in many studies to reduce opioid pain medication usage in patient care. Gabapentinoids (pregabalin and gabapentin) have historically been used to treat seizures, nerve pain, and anxiety. Current research, however, has successfully shown their effectiveness as pre- and post-operative pain medications. However, these studies have examined single-dose use of pregabalin/gabapentin in the management of postoperative pain and opioid consumption. As of yet, studies have not investigated the efficacy of multiple-dose administrations of these drugs on opioid consumption. The purpose of this study is to test the effectiveness of using multiple doses of pregabalin or gabapentin in combination with traditional opioid pain medications in order to decrease the amount of opioid pain medication usage in trauma patients. The primary outcome is to compare those receiving multiple doses of pregabalin vs. gabapentin vs. those receiving neither, and to determine daily average opioid requirement at 24 hour increments up to 7 days following initiation of study medication.

Word Count-163

Aims/Objectives

Primary Objective:

To determine if adding multiple doses of pregabalin or gabapentin upon admission will reduce opioid usage in trauma patients in the first 7 days of hospitalization or until discharge, if discharge < 7 days post-enrollment.

Secondary Objectives:

- I. To compare the change in documented incentive spirometry values from morning physical assessment among patients in each of the study groups who have at least 1 rib fracture. Decreased pain scores may correlate with improved incentive spirometry values, which may facilitate recovery from lung-related injury.
- II. To compare the proportion of patients requiring intubation among the study groups. Worsened pain is associated with respiratory distress which increases likelihood of intubation.
- III. To assess effectiveness of pain control in each arm based on the average Numeric Pain Rating Scale score per 24 hours following randomization. This scale is a 10 point numeric scale that ranges from 0 that represents "no pain" to 10 which indicates the "worst pain imaginable."
- IV. To evaluate the differences among the study arms with respect to hospital length of stay and unplanned ICU admissions.

Background

According to the Centers for Disease Control and Prevention, trauma is the fourth leading cause of death in the United States.¹ It is a major cause of mortality throughout the world. There are many factors that can affect morbidity and mortality in trauma patients including pain. Trauma introduces acute as well as chronic pain into the lives of its victims.² In a study by Gross and Amsler, severity of pain before and at least 2 years after poly-trauma, which was defined as patients with a well-defined injury of at least two body regions, was evaluated. After 2.7 ± 0.9 years following injury, only 54% of poly-trauma patients were fully rehabilitated. An astonishing 59% had to undergo a change in their occupation due to their injury(s). In addition, 2 years post-trauma 85% of these patients continued to experience pain.³ Literature suggest that 22% of the population experience chronic pain and more than one third of those cases are the result of trauma. Forty-six percent of long-term survivors of high energy trauma report daily pain after their trauma as compared to only 5% before the accident.²

Improved pain management in trauma patients leads to increased comfort as well as reduced morbidity and improved long-term outcomes.⁴ Successful approaches for achieving adequate pain control can vary greatly from patient to patient resulting in difficulty with the routine provision of analgesia. Pain in trauma patients can be a complicated process. Injury severity is often related to the level of pain experienced by trauma patients; however, pain alone can complicate a patient's condition and potentially lead to further clinical deterioration of the patient. Baseline physiology of trauma patients can widely vary from young athletes to elderly frail adults. Presenting with multiple injuries, substance use disorder, delayed care, as well as psychological and emotional issues can further complicate the care process. Understanding pain in trauma patients and how to manage it is crucial to their care.

The opioid crisis in the United States is a public health epidemic. Opioid overdose is a leading cause of injury-related death in the US and costs \$78.5 billion a year.^{5,6} West Virginia has been cited as having the highest rate of death due to drug overdoses (51.5 deaths per 100,000) by the CDC in 2018.⁷ Opioid tolerance occurs in individuals who consume opioids for long-term management of chronic pain, those who are or have been illicit users, or those who are enrolled in opioid substitution programs.⁹ Effective management of acute pain in opioid tolerant patients is more difficult. Analgesics may be required for a longer period of time and may deviate from the standard treatment protocols. In an article by Mehta and Lanford, it is discussed that if a patient presents with an opioid tolerance an alternative strategy may be needed to properly manage a patient's acute pain needs. When choosing pain medications, it is best to attempt the use of less addicting medications for the shortest period of time needed. Successful pain management in recovering addicts also poses unique challenges to providers as they struggle to decide if the patient is drug seeking or relapsing, which can be misinterpreted from tolerance.¹⁰

Pregabalin and gabapentin are controlled substances in the state of West Virginia, but they both are considered adjuvant analgesics which have analgesic properties.¹¹ By using multi-modal analgesia that targets different pathways of pain in the central and peripheral nervous system, individualized targeted patient therapy is provided.¹² In a trauma patient, whose pain is already difficult to control, this can be an alternative to typical opioid medications or used in conjunction to provide optimal patient centered pain control. Pregabalin and gabapentin are comparable in their mechanism of action, but the drugs differ in their pharmacokinetic and pharmacodynamic characteristics. Both drugs are absorbed by the gastrointestinal tract and are distributed across the blood brain barrier.¹³ Gabapentin is slowly absorbed with maximal plasma concentrations in 3-4 hours with oral administration. Pregabalin is absorbed much more rapidly with maximal plasma concentrations within 1 hour after oral administration. Both drugs decrease the release of neurotransmitters from brain tissues though the mechanism of action is not fully understood. Both are approved for treatment of neuropathic pain as well as partial seizures. With gabapentin, 50-75% of the dose (between 1800mg - 4800mg) are not absorbed. The bioavailability is enhanced by any agent that slows down transit time in the small intestines. Pregabalin, however, has greater than or equal to 90% systemic absorption and is not affected by agents which decrease gastrointestinal motility.¹⁴

There are several studies that support the efficacy of pregabalin and gabapentin in reducing pain when used alone or in conjunction with opioid pain medications. These studies have included evaluations of these agents for pre and postoperative pain management as well as post-traumatic pain.

^{12, 15, 16-18} Mishra et all conducted a study comparing pregabalin with gabapentin in chronic post thoracotomy pain. Pregabalin was given to patients one hour prior to their surgery and could be administered at lower doses because it has a higher bioavailability (90% vs 33-66%) and it is rapidly absorbed with its peak in 1 hour. The study concluded that pregabalin was an effective and safe adjuvant for reducing chronic post-thoracotomy pain in all age groups and gender without side effects.

Pain relief was statistically significant after three weeks of treatment and it continued till about six months.¹⁵ In another study, Arumugam, Lau, and Chamberlain examined postoperative opioid consumption in patients undergoing different abdominal and thoracic surgeries. They observed a significant decrease in opioid consumption when using gabapentin.¹² Eidy and colleagues designed a three arm study looking at gabapentin, pregabalin, or placebo effects on pain control in patients undergoing a laparoscopic cholecystectomy. A single pre-operative dose of gabapentin (800mg), pregabalin (150mg) and placebo were given. The study included 108 patients, with 36 in each group and concluded that gabapentin and pregabalin had significantly lower postoperative pain intensity scores than placebo. When compared to each other, pregabalin had significantly lower pain intensity scores than gabapentin. The placebo arm required significantly more postoperative analgesic therapy.¹⁶

Likewise, pregabalin and gabapentin has been used in management of post-traumatic pain. Gordh and associates looked at the use of gabapentin in traumatic nerve injury pain. When looking at the pain relief between the two treatment periods, more patients reported the pain had subsided by half during the gabapentin treatment (n=22) than during the placebo treatment (n=8). Gabapentin was more efficacious to placebo in providing pain relief by reducing the pain at least by half and improving the overall status of the patient reported by both clinician and the patient.¹⁷ Singh et al looked at the effectiveness of pregabalin in management of post-traumatic peripheral nerve injury not responding to other analgesics. The conclusions of both the case studies reviewed showed improved results.¹⁸

In conclusion, it is felt that trauma patients may benefit from the use of gabapentin or pregabalin in their pain control regimen. Pain management is a complicated process as patient's needs are individualized and so is their pain control requirements. Current studies have examined the effectiveness of preoperative single-dose or perioperative use of pregabalin/gabapentin in the management of postoperative pain and opioid consumption. As of yet, studies have not investigated the efficacy of extended administrations of these drugs on opioid consumption. Moreover, the majority of

the existing literature focuses on studies that have been conducted with patients having scheduled surgery and therefore administration of these drugs were standardized. Management of trauma patients on the other hand varies as patients present with varying injuries and requires individualized care plans. Accordingly, this study aims to reduce patients' consumption of narcotics in the hospital by utilizing multiple doses of adjunctive non-opioid analgesia for pain management in trauma patients.

Significance

The incidence of prescription opioid analgesic use has continued to increase and unfortunately the death rate from drug overdoses has shown a similar increase over the last several years. With alarming rates of drug-related deaths in West Virginia and the U.S. overall based on CDC data, it is crucial for clinicians to understand the impact that medical use of opioids may have on patients' mental and physical health. Especially, in the trauma patient population where opioid-based analgesia is commonly used to manage acute pain, it is important to treat the patient's pain without adding to the already growing problem. It is important for practitioners to be mindful and try to prescribe the lowest most effective dose needed to optimally control pain. Use of adjunctive analgesics may help lessen the amount of opioids prescribed and help the patient on their path of healing not just physically, but also emotionally and mentally.

Methodology

Study design

This will be a prospective, randomized trial with patients admitted to Charleston Area Medical Center's (CAMC) Trauma Services under the care of Nurse Practitioners (NPs) with attending supervision. Patients included in this study will be separated in three groups: Group A: Patients will be started on gabapentin upon admission after consented. They will receive 300 mg PO every 8 hours without dose titration. Group B: Patients will be started on pregabalin upon consent. They will receive 50 mg every 8 hours without dose titration. Group C: Patients in this group will be neither on gabapentin

nor pregabalin upon consent. In Groups A and B, patients with CrCl < 60mL/min will receive same dose given q12 hours. The q12 hour regimen may be increased to q8 hours if CrCl increases above 60mL/min during the 7 days study period or until discharge (if < 7 days post-enrollment).

Inclusion Criteria

1. NP service admissions
2. 18 year of age and older
3. Patients enrolled within 36 hours of admission
4. Anticipated duration of hospitalization >24 hours from time of consent
5. Active order(s) for opioids in place at the time of enrollment

Exclusion Criteria

1. Clinician discretion based on patient care management
2. Intubated patients
3. Patients with epidural or peripheral nerve block
4. Patients with pregabalin/gabapentin as home medications
5. Patients receiving pregabalin/gabapentin upon admission
6. Traumatic brain injury patients
7. CrCl<30ml/min or on HD
8. Unable to take enteral medications
9. On Patient Controlled Analgesia (PCA)
10. Patients with complicated wound closure
11. History of epilepsy
12. Documented history of substance use disorder (this exclusion criterion was chosen to provide consistency among the study population as pain management may differ among these patients)

Setting

Charleston Area Medical Center's General Hospital, a Level 1 Trauma Center.

Sample Size

A sample size of 70 patient per study group which includes 10% attrition will be targeted (a total of 210 patients). This is based on Cohen's *d* formula with a significance of 0.05, 80% power and a medium effect size. Previous studies have evaluated the impact of single dose administration of pregabalin and gabapentin on pain and opioid consumption and were mostly conducted with patients having scheduled surgery. The current study, however, is designed to examine the effectiveness of multiple doses of these drugs in acutely injured trauma patients. Therefore, past reliable data could not be used for the power calculation for this study and Cohen's *d* coefficient was used for effect size. A medium effect size, which indicates a 69% difference between treatment and control groups was set by clinicians. For sample size estimation, instead of using effect size for the overall ANOVA which tests a general hypothesis we utilized effect sizes for the planned comparisons [(pregabalin vs. gabapentin); (pregabalin vs. neither pregabalin nor gabapentin); (gabapentin vs. neither pregabalin nor gabapentin)] using t-statistic.

Procedure/Protocols

Pre-intervention

- The clinical research coordinator will review the investigator's census on a daily basis in order to identify new admissions who may be study candidates.
- All patients who are eligible will be informed about the study. Patients with capacity who agree to participate will be consented using the consent form as written within 24 hours of admission. A note will be made in the patient's chart detailing the consent.

- A randomization schedule will be generated using a SPSS algorithm. Patients will be assigned a study number and allocated to a respective study arm in order as they are consented.
- Both pregabalin and gabapentin are frequently used as adjunct analgesia in this patient population at CAMC. Thus, there will be no additional cost for participating in the study. However, blinding would not be in the best interest of the study because the design of these medications are identifiable to the trauma providers and it will be costly to get them blinded for this study. The patient will sign and date the consent and the HIPAA authorization form (which will be attached to the consent). Each patient will be assigned a patient study number and randomized accordingly to a pre-determined study arm.
- Original signed consent will be kept and stored in a binder at the CAMC Trauma Research Office. A copy of the consent form will be placed in the patient's chart and another will be given to the participant.

Intervention

- Patients in the pregabalin group will receive 50 mg q8 without dose titration. Patients in the gabapentin group will receive 300 mg q8 without dose titration. Patients enrolled with CrCl < 60mL/min will receive same dose given q12 hours.
- Adjunctive non-opioid analgesia, i.e. non-steroidal anti-inflammatory agents, may also be added at the managing service's discretion. Non-narcotic analgesia as adjunctive therapy may be added at the managing service's discretion. Total daily acetaminophen dose is not to exceed 3 gm.
- Following enrollment, the patients' opioid analgesia regimen may be increased or decreased at the managing service's discretion. Narcotic analgesic can be increased or decreased by 2.5 mgs of oxycodone or equivalent (i.e. oxycodone 5 mg q4 hrs as needed

to 7.5 mg oxycodone q4 hrs as needed) or increasing the dose of intravenous morphine by 2 mgs or equivalent.

- Decreasing dose of the opioids is at the discretion of the managing service.
- Patients with pre-existing narcotic use will be placed on their home regimens or an intravenous equivalent using a standardized dosing conversion table and adjustments can be made at the discretion of the managing service.

Data Collection

Data will be collected via patient chart review and institution's trauma registry. Data will be collected in an Excel spreadsheet. The following data will be collected for each patient:

- Demographics
 - Gender
 - Age
 - Height
 - Weight
 - Date & time of hospital admission and discharge
 - Comorbidities
- Urine and drug screen
- Admitting injury list
- Length of Stay
- Pre-existing (home) analgesic regimens
- Prior exposure of pregabalin or gabapentin
- Surgery dates and surgeries performed
- Inpatient analgesic exposure prior to enrollment (medications, dose, # of doses) and 7 days post-enrollment or until discharge (if < 7 days post-enrollment)

- Initial Incentive Spirometry value and 7 days post enrollment or until discharge (if < 7 days post-enrollment)
- Documented pain scores for each 24-hour period post-enrollment for 7 days or until discharge (if < 7 days post-enrollment)
 - Additional notation will be made to indicate the first pain score that coincides with the initiation of study medication
- Post-enrollment complications (unplanned intubation, unplanned ICU admission, incidence of VTE, infection, pneumothorax requiring chest tube placement, other)
- Post enrollment daily creatinine value from Basic Metabolic Panel
- Side effects including somnolence, dizziness, fatigue, ataxia, tremor, amnesia and others

Data Analysis

Descriptive analysis will be conducted for each variable in this study. Means and standard deviations or medians and interquartile ranges for continuous variables will be reported. For categorical variables, proportions and frequencies will be computed. To assess statistically significant difference between two cohorts, t-tests or Mann-Whitney U will be conducted for continuous variables. Categorical variables will be compared using chi-square or Fisher's Exact test. Outcome variables will be analyzed with ANCOVA or binary logistic regression controlling for differences in patient characteristics. A sub-analysis will be conducted by examining outcomes based on the number of days patients stay in the hospital post-enrollment. All comparisons will be performed at a level of significance of $p \leq 0.05$. Analysis will be done using 22.0SPSS version.

Subject Population

There are no known vulnerable participants to be included (specifically those under 18, prisoners, or those with pre-existing cognitive defects).

Benefits

Our study might show that pregabalin and gabapentin as adjunctive non-opioid analgesia may significantly reduce opioid usage in trauma patients, which will perhaps lessen complications related to use of opioids in trauma patients.

Risks and Discomfort

Both pregabalin and gabapentin are routinely used as adjunctive non-opioid analgesia by NPs in trauma patient care; and therefore, there is no added risk to their standard care regimen.

Consent Process

All patients who are eligible will be informed about the study. Patients will be informed that their participation is completely voluntary and whether they decide to participate or not will in no way affect their current or future relationship with their attending physicians, residents, or staff at Charleston Area Medical Center (CAMC). Furthermore, they will be also informed that they have the right to withdraw from the research at any time without penalty.

Patients with capacity who agree to participate will be consented using the consent form as written within 36 hours of admission. A note will be made in the patient's chart detailing the consent. The patient will sign and date the consent and the HIPAA authorization form (which will be attached to the consent). Each patient will be assigned a patient study number and randomized accordingly to a pre-determined study arm. Original signed consent will be kept and stored in a binder at the CAMC Trauma Research Office. A copy of the consent form will be placed in the patient's chart and another will be given to the participant.

Confidentiality

Any documents with study information will be kept in a locked office. Patient FIN will be linked to the study number so that we can ensure full data extraction without compromising the patients' privacy. Any electronic data will contain minimal PHI or no PHI. All electronic data will be password protected and can only be accessed by study personnel.

Costs/Payments

The patient will be responsible for all co-pays and deductibles associated with routine care billable to insurance and/or them. There will be no additional financial burden to the patient for participating in the study.

Payment to Subjects

None

Investigators

Primary Investigator: [name] APRN, CNP

Co-Investigators: [name], BCCCP, MBA

Other Participants/Research Support

- [name]-BC, MS
- [name], MS

References

1. Centers for Disease Control and Prevention. Accidents or Unintentional Injuries. Retrieved November 2020, <https://www.cdc.gov/nchs/fastats/accidental-injury.htm>

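### Secondary Objective I: fix the initial spirometry value as a covariate, because the planned ANCOVA does not name it and appears to choose covariates by observed differences

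*Combined protocol and SAP*

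**What the plan says.** Secondary Objectives, I, sets the outcome: "To compare the change in documented incentive spirometry values from morning physical assessment among patients in each of the study groups", restricted to those "who have at least 1 rib fracture". Data Collection lists "Initial Incentive Spirometry value and 7 days post enrollment", or until an earlier discharge, so a baseline value will be on file. Gender, age and height are listed under Demographics in the same section.

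Data Analysis has two rules that could apply to this outcome. One is adjusted: "Outcome variables will be analyzed with ANCOVA or binary logistic regression controlling for differences in patient characteristics". The other is unadjusted: "To assess statistically significant difference between two cohorts, t-tests or Mann-Whitney U will be conducted for continuous variables". No covariate is named for any outcome, the initial spirometry value is not mentioned as one, and the section does not say which rule governs spirometry. The documents give no expected number of patients with rib fracture.

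**The concern.** The outcome is worded as a change, and the only adjustment rule is tied to differences in characteristics. That reads most naturally as adjusting for whatever is found to differ between arms. On that reading the initial spirometry value enters the model only if it happens to look imbalanced, whereas the reason to include it is that it predicts the later value. A t-test or Mann-Whitney U on raw change would also comply with the section.

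Subtracting the initial value amounts to assuming that the later value rises one-for-one with it. If the true slope is not 1, the subtraction adds noise that a fitted slope would remove. An ANCOVA on change that adjusts for other characteristics but leaves out the initial value keeps this noise, apart from what those characteristics happen to explain.

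At stake is precision in a subset that cannot exceed the full arm and for which the trial was not sized. Leaving covariates to be chosen after the data are seen, in an open-label trial, also gives avoidable freedom in the analysis.

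**Working it through.** **Inputs from the protocol (Sample Size).** Alpha 0.05, power 80%, a medium effect, 70 per group including 10% attrition. The plan's own figure reproduces with d = 0.5, two-sided: n = 2 × (1.960 + 0.842)² / 0.5² = 62.8, so 63 per group, and 63 / 0.9 = 70. Evaluable per arm is therefore 63.

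**Assumptions, not in the documents.** Correlation rho between initial and later value (0.5 to 0.9); share with rib fracture (20% to 50%, giving 13, 19, 25 or 32 per arm); equal SDs at both times; true arm difference of 0.5 SD of spirometry.

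**Variances.** Let s1 and s2 be the SDs of the initial and later value, and b = rho × s2/s1 the slope of later on initial.
- Raw change: s1² + s2² − 2 × rho × s1 × s2.
- Adjusted for the initial value: s2² × (1 − rho²).
- The difference between them is s1² × (1 − b)². It is never negative and is zero only when b = 1.

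With equal SDs set to 1, these become 2(1 − rho) and 1 − rho², with ratio (1 + rho)/2:
- rho 0.5: 0.75 / 1.00 = 0.75
- rho 0.7: 0.51 / 0.60 = 0.85
- rho 0.8: 0.36 / 0.40 = 0.90
- rho 0.9: 0.19 / 0.20 = 0.95

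**Power.** Two-sample t-test, two-sided 0.05, standardised difference 0.5 divided by the square root of the variance above. Each cell is raw change → adjusted (gain in points).

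| Rib-fracture share (n per arm) | rho 0.5 | rho 0.7 | rho 0.9 |
|---|---|---|---|
| 20% (13) | 23.2 → 29.3% (6.1) | 35.2 → 40.3% (5.1) | 78.1 → 80.1% (2.0) |
| 30% (19) | 32.3 → 41.0% (8.7) | 49.1 → 55.6% (6.5) | 91.8 → 93.1% (1.3) |
| 40% (25) | 41.0 → 51.6% (10.6) | 60.9 → 67.9% (7.0) | 97.2 → 97.8% (0.6) |
| 50% (32) | 50.4 → 62.3% (11.9) | 72.0 → 78.7% (6.7) | 99.3 → 99.5% (0.2) |

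**Small-sample cost of estimating the slope.** In a two-arm comparison the adjusted variance is inflated on average by 1 + 1/(2n − 4). At 13 per arm this is 1 + 1/22 = 1.045, so the ratio becomes 0.75 × 1.045 = 0.78 at rho 0.5 and 0.95 × 1.045 = 0.99 at rho 0.9. In the smallest subset with the highest correlation, the gain is therefore close to nil.

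**A case with no gain.** If rho = 0.8 and the later SD is 1.25 times the initial SD, b = 0.8 × 1.25 = 1. Raw change has variance 1 + 1.5625 − 2 = 0.5625; adjusted, 1.5625 × 0.36 = 0.5625.

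**Later value or change as the response.** With the initial value in the model, replacing the later value by the change only lowers the fitted slope by 1. The arm difference and its standard error are identical, so the word change in the objective need not be altered.

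**The case against.** The strongest reply is that ANCOVA is already planned for outcome variables, that spirometry is a continuous outcome, and that an objective names an endpoint rather than a model. This stands. A reader might infer from the objective that spirometry will be compared with no adjustment, but the documents do not support that. They support only that adjustment for the initial value is not specified. Nor can one say that height, age and gender go unused: they are patient characteristics that the planned ANCOVA could include. How much of the gain above the sponsor's ANCOVA would already capture cannot be determined, because its covariates are not named. The table compares the fix with an unadjusted test of change, so it shows the most the fix would add over such a test.

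A reader might also count chance baseline imbalance as a second harm. At 25.2 per arm (40% of 63), one standard error of the baseline gap is √(2/25.2) = 0.28 SD, which moves a change-score difference by (1 − 0.5) × 0.28 = 0.14 SD at rho 0.5. That is the same excess variance, (1 − rho)² with equal SDs, seen from another side. Under randomisation the change score is unbiased on average.

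It is fair, too, that the gain rests on undocumented inputs, disappears when the slope is 1, and concerns one secondary outcome. These points limit the size of the finding. They give no reason to prefer leaving the initial value out.

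**Conclusion.** The point holds as a precision and pre-specification matter. As written, the plan does not ensure that the initial spirometry value enters the analysis of Objective I, and it allows an unadjusted test of change. Fixing that value as a covariate lowers the variance by 5% to 25% for rho 0.9 to 0.5 with equal SDs, before the small cost of estimating the slope. In power this is about 6 to 12 points at rho 0.5, 5 to 7 at rho 0.7 and 2 or less at rho 0.9, over rib-fracture shares of 20% to 50%. Rho, the share, the equal SDs and the 0.5 SD difference in spirometry are assumptions. Even after the change, power stays below 80% throughout the table at rho 0.5 and 0.7. The primary outcome is not affected. This is a free improvement, not an error that invalidates the comparison.

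**What to change.** Add to Data Analysis that, for Secondary Objective I, the governing analysis in patients with rib fracture is an ANCOVA of spirometry (later value or change) on study arm, with the initial value as a covariate fixed in advance whatever imbalance is observed. Report the adjusted arm differences with 95% confidence intervals, and state that the t-test or Mann-Whitney U is not the governing analysis for this outcome. Height, age and gender may be added as fixed covariates, but they probably add little once the initial value is in the model. The statement should also say which later value is used, since values run for up to 7 days or until discharge; a change score needs the same definition.

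The cost is a short addition to the text and one degree of freedom for the initial value, or four with height, age and gender. All the data are already being collected.

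### The incentive spirometry change has no common time point, and its follow-up ends at discharge, which is itself an outcome compared by arm

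*Combined protocol and SAP*

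**What the plan says.** Secondary objective I is "To compare the change in documented incentive spirometry values from morning physical assessment" and restricts this to patients "among patients in each of the study groups who have at least 1 rib fracture". It names no day, no summary of the daily readings and no rule for patients who leave early. By contrast, the primary outcome is given in 24-hour steps and pain (objective III) as an average per 24 hours.

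The only time window for spirometry is an item in the Data Collection list: "Initial Incentive Spirometry value and 7 days post enrollment or until discharge (if < 7 days post-enrollment"). Inclusion criterion 4 asks only for "Anticipated duration of hospitalization >24 hours from time of consent".

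Stay is itself an outcome. Objective IV is "To evaluate the differences among the study arms with respect to hospital length of stay and unplanned ICU admissions".

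On method, Data Analysis says: "Outcome variables will be analyzed with ANCOVA or binary logistic regression controlling for differences in patient characteristics". It then adds: "A sub-analysis will be conducted by examining outcomes based on the number of days patients stay in the hospital post-enrollment". The documents give no spirometry mean, standard deviation (SD) or daily trend, no expected stay and no count of rib-fracture patients.

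**The concern.** Values stop at discharge, and the anticipated stay need only exceed 24 hours. A patient's change can therefore cover anything from about 1 to 7 days. How long it covers is decided after randomisation and may depend on the drug.

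If the analyst takes the last in-hospital value minus the initial value, which the text permits, the arm comparison mixes two things: how fast patients recover per day and how long they were observed. Arms with identical daily recovery could then differ, or a real difference in recovery could be hidden. Because the measure is not fixed in advance, the choice could also be made after the data are seen.

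There is a smaller point on precision. The initial spirometry value is collected but is not named as a covariate.

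**Working it through.** **Plan's own figure.** There is none for spirometry. The 70 per group in Sample Size does not concern this endpoint.

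**Inputs from the documents.** Collection runs to day 7 or discharge (Data Collection); anticipated stay exceeds 24 hours (inclusion criterion 4); stay is compared by arm (objective IV).

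**Assumed inputs, for illustration only.** Linear change of *b* mL/day; change scored as last in-hospital value minus initial value; observed follow-up *L* limited to 1 to 7 days; 30 rib-fracture patients per arm; reading SD 200 mL. The last two affect precision, not the bias.

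**Step 1: same recovery, different stay.** With *b* the same in both arms and discharge unrelated to it:

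expected difference = *b* × (mean *L* in the shorter-stay arm − mean *L* in the other arm)

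A one-day gap in stay shrinks to about 0.78 to 0.94 day once stays are limited to 1 to 7 days; the exact figure depends on how spread out stays are. Then:

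- *b* = +100: 100 × (−0.78 to −0.94) = −78 to −94 mL. The shorter-stay arm looks worse.
- *b* = 0: 0 mL.
- *b* = −30: −30 × (−0.78 to −0.94) = +23 to +28 mL, or +26 mL at the middle value of 0.86 day. The shorter-stay arm looks better.

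The true difference in daily recovery is zero in all three.

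**Step 2: faster recovery and shorter stay together.** Take mean observed follow-up of 3.88 against 4.63 days.

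- 120 against 100 mL/day: 120 × 3.88 − 100 × 4.63 = 465.6 − 463 = +2.6 mL (simulated +2). The true day-3 difference is 3 × 20 = +60 mL, so the benefit is almost wholly masked.
- 150 against 100 mL/day: 582 − 463 = +119 mL, against a true day-3 difference of 3 × 50 = +150 mL. The benefit is diluted but not reversed.

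**Step 3: discharge triggered by recovery.** If patients leave once they reach a target gain, a simulation at 120 against 100 mL/day gives +27 mL by last value, against +60 mL true at day 3. In the same setting, comparing only those still in hospital on day 5 gives +51 mL against +99 mL true. A fixed day therefore helps only if most patients reach it or early discharge is handled explicitly.

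**Step 4: the planned remedies.** ANCOVA on patient characteristics contains no term for time, and adjusting for the initial value would not correct unequal follow-up either. The sub-analysis groups patients by days in hospital. If the drug alters stay, patients in the same stratum of different arms are no longer comparable by randomisation.

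**Step 5: precision.** With equal variances σ² and correlation ρ between initial and later value, the variance is 2σ²(1 − ρ) for raw change and σ²(1 − ρ²) after adjustment. The ratio is (1 + ρ)/2:

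- ρ = 0.7: 0.85, a 15% reduction.
- ρ = 0.5: 0.75, a 25% reduction.

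**The case against.** The strongest reply is that the plan never says change means last minus initial. The window comes from a list of what is recorded, not from a definition of the endpoint. A day-by-day comparison, a slope or a fixed-day difference fits the text equally well. This stands, and it limits the point: what the documents show is an undefined measure with an outcome-dependent window, not a commitment to a biased score.

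A reader might infer that a drug which shortens stay would necessarily look worse. The documents do not support that. It would need last-value scoring, values that rise during the stay, and a shortening large enough to outweigh any faster recovery. The protocol's own expectation that less pain goes with better spirometry makes rising values plausible, but it gives no trend. Flat values produce no bias and falling values reverse it.

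The sponsor can also say that the sub-analysis by days in hospital already deals with unequal stays. It shows that the issue was seen. It does not settle it, because the grouping variable is post-randomisation and the rib-fracture subset is of unstated size.

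Finally, every magnitude here rests on assumed inputs. That is correct. No false-positive rate is given, because it depends strongly on the spread of stays, which the documents do not report.

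**Conclusion.** The point holds in limited form. Objective I sets no common time point, its values end at day 7 or discharge, and stay is compared by arm, so length of follow-up depends on an outcome. If change is scored to the last in-hospital value, a one-day difference in stay could produce an apparent difference of several tens of mL with no difference in daily recovery, or hide a real one. The direction is not determined by the documents. The figures assume linear change and a one-day gap in stay; the 15% to 25% variance reduction assumes equal variances and correlations of 0.7 to 0.5.

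This concerns a secondary endpoint in a subgroup. It is a worthwhile refinement and does not threaten the primary objective.

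**What to change.** In Data Analysis, state that the daily morning spirometry values will be analysed with a linear mixed model containing arm, day, arm-by-day and the initial spirometry value as covariate. Report the arm difference at one pre-specified common day that most patients reach. The model uses each patient's readings up to discharge; state its assumption that discharge depends only on observed values and covariates.

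The minimum version is ANCOVA of the value at that day on arm and initial value, with a stated rule for patients discharged before it.

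The sponsor should choose the day. A very early day, such as day 1, keeps nearly everyone but may be too soon to show an effect of multiple doses. A late day is reached by fewer patients, and those remaining may be selected. Keep the sub-analysis by days in hospital as descriptive only.

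The cost is a few lines of text. The readings come from morning assessments already charted, but extraction must take each morning's value and not just the first and last. The fixed-day version gives up some information on later recovery.
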